9.2.2. Exclusion criteria

Patients meeting any of the following criteria will not be included in the study:

1. Had a record of VTE diagnosis (ICD-10: I26.0, I26.9, I80.2, I80.3) within the 12-month period prior to the index VTE encounter.
2. Diagnosed with atrial fibrillation/flutter (ICD-10: I48), mechanical heart valve replacement (National Procedure Code: Z952, M6531, M6532, M6533, O1781, O1782,

O1783, O1791, O1792, O1793, O1797, O1794, O1795, O1796, O1798, O1799) or mitral stenosis (ICD-10: I05.0, I05.2) anytime prior to index date

3. Had a record of Inferior Vena Cava filter (National Procedure Code: O2045, M6650) anytime prior to index date
4. Received anticoagulatory therapy within the 12-month period prior to index VTE encounter to restrict to new users of anticoagulatory therapy.
5. Prescribed two different anticoagulants on the same index date to prevent exposure misclassification.
6. Had a record of pregnancy (ICD-10: O03-O07, O10-O14, O16, O20-O026, O28-O36, O41-O43, O46.8, O46.9, O61-O66, O67.8, O67.9, O69, O70-O75, O80-O92, O94-O99, P08, Z33-Z39) within the 9-month period prior to index date
7. Had a record of active cancer, defined as first diagnosis of cancer (ICD-10: C00-C97 [excluding non-melanoma skin cancer: C44]) with V code (V011, V027, V193, V194; a special code applied to patients with confirmed diagnosis of cancer by Korean Ministry of Health and Welfare for reimbursement for 5 years or longer if recurrent/metastasis) within the past 6 months of period prior to index date; or receiving anti-cancer treatment (chemotherapy, radiation therapy, or cancer-related surgery) under cancer diagnosis with V code within the past 6 months from index date (for Phase II of the study only). WHO-ATC codes and National Procedure Codes for anti-cancer treatment are shown in Table 1.

Table 1. WHO-ATC codes and National Procedure Codes for anti-cancer treatment

Anti-cancer treatment	WHO-ATC codes / National Procedure Codes
Chemotherapy	L01-04, H02AB02, H02AB04, H02AB06, H02AB07, H02AB09
Radiation therapy	HD051-HD059, HD061, HD071-HD073, HD080-HD089, HD091-HD093, HD110-HD115, HD121, HD150, HD160, HD211, HD212, HZ271

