8.3.2. Exclusion criteria

Patients meeting any of the following criteria will not be included in the study:

1. Had a record of VTE diagnosis (ICD-10: I26.0, I26.9, I80.2, I80.3) within the 12-month period prior to the index VTE encounter.
2. Diagnosed with atrial fibrillation/flutter (ICD-10: I48), mechanical heart valve replacement (National Procedure Code: Z952, M6531, M6532, M6533, O1781, O1782, O1783, O1791, O1792, O1793, O1797, O1794, O1795, O1796, O1798, O1799) or mitral stenosis (ICD-10: I05.0, I05.2) anytime prior to index date.
3. Had a record of Inferior Vena Cava filter (National Procedure Code: O2045, M6650) anytime prior to index date.
4. Received anticoagulatory therapy within the 12-month period prior to index VTE encounter to restrict to new users of anticoagulatory therapy.
5. Prescribed two different anticoagulants on the same index date to prevent exposure misclassification.
6. Had a record of pregnancy (ICD-10: O03-O07, O10-O14, O16, O20-O026, O28-O36, O41-O43, O46.8, O46.9, O61-O66, O67.8, O67.9, O69, O70-O75, O80-O92, O94-O99, P08, Z33-Z39) within the 9-month period prior to index date.

7. Had a record of active cancer, defined as first diagnosis of cancer (ICD-10: C00-C97 [excluding non-melanoma skin cancer: C44]) with V code (V011, V027, V193, V194; a special code applied to patients with confirmed diagnosis of cancer by Korean Ministry of Health and Welfare for reimbursement for 5 years or longer if recurrent/metastasis) within the past 6 months of period prior to index date; or receiving anti-cancer treatment (chemotherapy, radiation therapy, or cancer related-surgery) under cancer diagnosis with V code within the past 6 months from index date (for Phase II of the study only). WHO-ATC codes and National Procedure Codes for anti-cancer treatment are shown in below table.

Anti-cancer treatment	WHO-ATC codes / National Procedure Codes
Chemotherapy	L01-04, H02AB02, H02AB04, H02AB06, H02AB07, H02AB09
Radiation therapy	HD051-HD059, HD061, HD071-HD073, HD080-HD089, HD091-HD093, HD110-HD115, HD121, HD150, HD160, HD211, HD212, HZ271

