Cancer-related surgery	N0232, N0284-N0286, NA281-NA284, N0335, N0404, N0405, N0435-N0437, N0940, O0961-O0963, O1045, O1047, O1048, O1224-O1227, O1251, O1252, O1401, O1403-O1405, O1410, O1421-O1424, O1431, O1432, O1471, O1484, O1486, O1572, O1592, O1596, O1982, P2091, P2093, P2123, P2124, Q2150, Q2181-Q2183, Q2203, Q2206, Q2232, Q2292-Q2294, Q2346, Q2347, Q2348, Q2361, Q2362, Q2363, Q2365-Q2369, Q2401, Q2402, Q2403, Q2502, QA536, Q2533, Q2534, Q2536, Q2537, Q0251-Q0259, Q2594, Q2598, Q2601, Q2650, Q2651, QA671-QA673, QA679, Q1261, Q1262, Q2671-Q2673, Q2679, Q2761, Q2762, Q2791-Q2794, Q2796-Q2798, Q2890-Q2893, Q2901, Q0292, Q2921-Q2924, Q2927, Q2928, QA921-QA924, QA928, Q2925, Q2926, QA925, QA926, R3271, R3273, R3274, R3275, R3290, R3305, R3307, R3299, R3300, R3309, R3310, R3432, R3433, R3451, R3470, R3481, R3482, R3541-R3543, R3530, R3590, R3755, R3756, R3791, R3792, R3801, R3802, R3851, R3853, R3861, R3862, R3891, R3901, R3902, R3950, RZ512, R3960, R3975, R4003, R4004, R4067, R4068, R4071-R4074, R4140, R4143, R4144, R4147-R4149, R0141, R0142, R4154, R4155, R4156, R4250, R4331, R4332, R4423-R4428, P4543, P4551-P4554, P4561, P4571, P4572, S4616, S4634-S4639, S6691-6696, S4694-S4696, S4707-S4709, S4743, S4756-S4758, S4780, S4801-S4803, S4880, S4900, S4950, S5200, S5220, S5231, S5232, S5246, S5592, S5745, M6774, M6870, M6880, M6775, QZ841, M6890, M6900, M6991, M6910, Q0841, Q0842, N7136-N7139, N7140-N7153, Q7221-Q7225, Q7230, Q7280-Q7285, Q7342,

PFIZER CONFIDENTIAL

	Q7380, Q7410, Q7561-Q7567, Q7571, Q7572, Q7651-Q7654, Q7701-Q7703, QX706, Q7751, Q7752, Q7761-Q7763, Q7766, Q7771, Q7772, Q7775, Q7788, Q7789, U4811, U4812, U4881-U4883
Others	X5131-X5137 (hemopoietic cell transplantation)

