- If a patient has evidence of a repeat prescription within 30 days of the end of their prescription and does not experience any of the above events (treatment interruption, switch, or discontinuation), they will be assumed to be persistent on treatment.[1]
- Clinical event preceding first treatment change will be defined as occurrence of any event listed below within 30 days before treatment interruption, switch, or discontinuation. A new clinical event will be considered 'new' when it occurs for the first time within a 6-month period for acute conditions (arterial thromboembolism, ischemic stroke, transient ischemic attack, myocardial infarction, angina pectoris, acute kidney injury, and abnormal liver function) and 5-years for chronic conditions (cancer, chronic kidney disease, and liver disease). A patient may contribute to multiple events.
 - ① Major bleeding (as defined in Phase II)
 - ② Complications of VTE: post-thrombotic syndrome and chronic thromboembolic pulmonary hypertension
 - ③ Thromboembolism: PE diagnosis in patients with index event as DVT only, new diagnosis of arterial thromboembolism, ischemic stroke, transient ischemic attack, myocardial infarction, or angina pectoris
 - ④ Major surgery: orthopedic surgeries (knee arthroplasty, hip arthroplasty, and hip fracture surgery), cancer surgeries (stomach, colorectal, hepatobiliary, pancreatic, breast, ovarian, cervical, renal, bladder, prostate, lung, and esophageal cancers, and brain tumors), and benign surgeries (myomectomy, oophorectomy, and transurethral resection of the prostate)
 - ⑤ Cancer-related event (among non-active cancer patients only): new diagnosis of active cancer
 - ⑥ Kidney function change: new diagnosis of chronic kidney disease or acute kidney injury
 - ⑦ Liver function change: new diagnosis of liver disease or abnormal liver function

Clinical event preceding first treatment change	ICD-10 diagnosis code
Major bleeding	Defined in Phase II
Complications of VTE	
Post-thrombotic syndrome	I87.0
Chronic thromboembolic pulmonary hypertension	I27.2
Thromboembolism	
PE diagnosis	I26.0, I26.9
Atrial thromboembolism	I74
Ischemic stroke	I63
Transient ischemic attack	G45.9
Myocardial infarction	I21
Angina pectoris	I20
Major surgery	
Orthopedic surgeries	N0305, N0601, N0611, N0641, N0711, N2070, N0715, N2710, N0731, N0981, N0991, N1711, N3710, N1721, N3720, N1715, N4710, N1725, N4720, N2072, N2077, N2712, N2717, N3712, N3717, N3722, N3727, N4712, N4717, N4722, N4727

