Cancer surgeries	Specified in 'cancer-related surgery' of section 8.3.2
Benign surgeries	R4123-R4129, R4421, R4430, R3975
Cancer-related event (active cancer)	C00-C97 (excluding non-melanoma skin cancer, C44) with V code (V011, V027, V193, V194)
Kidney function change	
Chronic kidney disease	N18, N19
Acute kidney injury	N17
Liver function change	
Liver disease	B15-B19, K70-K77
Abnormal liver function	R94.5, R74.0

- **Phase II of the study**

- Major bleeding will be defined using primary or secondary diagnosis codes according to the ICD-10 diagnostic codes shown in below table and classified by site (intracranial, gastrointestinal [GI], all others).

Major bleeding	ICD-10 diagnosis code	Diagnostic definition
Intracranial hemorrhage	I60, I61, I62, I690, I691, I692, S064, S065, S066, S068	Diagnosis code + admission code + brain CT or MRI code

		* Brain CT or MRI: CT: HA441, HA451, HA461, HA471, HA851 MRI: HE101, HE102, HE135, HE201, HE202, HE235, HE301, HE302, HE401, HE402, HE501, HE502, HE535
GI bleeding	I850, I983, K2211, K226, K228, K250, K252, K254, K256, K260, K262, K264, K266, K270, K272, K274, K276, K280, K282, K284, K286, K290, K3181, K5521, K625, K920, K921, K922	Diagnosis code + admission code
Other bleeding	D62, H448, H3572, H356, H313, H210, H113, H052, H470, H431, I312, N020-N029, N421, N831, N857, N920, N923, N930, N938, N939, M250, R233, R040, R041, R042, R048, R049, T792, T810, N950, R310, R311, R318, R58, T455, Y442, D683	Diagnosis code + admission code

- The earliest date of diagnosis of the major bleeding event after the index date will be defined as the outcome occurrence date.
- Patients will be followed up from the index date to the occurrence of an outcome, treatment discontinuation (30-day grace period), switch to another anticoagulants, in-hospital death, or end of the study period (31 Dec 2019) whichever comes first.

Potential Confounder(s)

- Sociodemographic characteristics such as age, sex, and index year will be assessed at the index date.
- CCI [2] and HAS-BLED [3] scores will be measured within the 6-month period prior to the index date.

List of CCI	Score	ICD-10 codes
Cerebrovascular disease	1	G45, G46, H34, I60-I69
Congestive heart failure	1	I09.9, I11.0, I13.0, I13.2, I25.5, I42.0, I42.5-I42.9, I43, I50, P29.0
Chronic pulmonary disease	1	I27.8, I27.9, J40-J47, J60-J67, J68.4, J70.1, J70.3

Dementia	1	F00–F03, F05.1, G30, G31.1

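### The Phase I definition of cancer surgery omits the V-coded cancer diagnosis required for the same codes elsewhere, and procedure code R3975 falls under both cancer and benign surgery

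*SAP*

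**What the plan says.** The secondary objective of Phase I is to explore clinical events that precede a change from the index anticoagulant (SAP section 6). SAP 8.4 lists major surgery as one event type, looked for in the 30 days before interruption, switch or discontinuation. It has three sub-types: orthopedic, cancer and benign surgery. Cancer surgery is described by 13 sites (12 named cancers plus brain tumors) and benign surgery by three named operations.

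The code table in 8.4 turns this into rules:

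- Cancer surgeries: "Specified in 'cancer-related surgery' of section 8.3.2".
- Benign surgeries: "R4123-R4129, R4421, R4430, R3975".

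In SAP 8.3.2, exclusion criterion 7 uses the cancer-surgery codes as part of the active-cancer definition: "receiving anti-cancer treatment (chemotherapy, radiation therapy, or cancer related-surgery) under cancer diagnosis with V code". Protocol 9.2.2 sets the same condition: "cancer-related surgery) under cancer diagnosis with V code within the past 6 months from index date". The codes follow in a separate table, introduced by "WHO-ATC codes and National Procedure Codes for anti-cancer treatment are shown in below table". Its row labelled cancer-related surgery contains procedure codes only, among them "R3960, R3975, R4003, R4004".

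**The concern.** The diagnosis condition stands in the sentence of criterion 7, not in the code row. The 8.4 pointer uses the label of the code row and adds no condition. A programmer who follows it literally would count any listed procedure as cancer surgery, with or without a cancer diagnosis.

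The plan itself shows that this matters for at least one code, because it lists R3975 as benign surgery too. SAP section 10 gives the purpose of the analysis as identifying potential reasons for treatment change, and describes patients with and without active cancer separately. In the cohort without active cancer, an R3975 operation for benign disease would appear as a cancer operation before a stop or switch. A reader could then take malignancy as the reason where the data do not show one.

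**Working it through.** No sample size, power or alpha figure is involved, and the plan states no figure to reproduce. The check is a comparison of the code lists and of the two possible readings of the pointer.

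**1. Overlap of the lists.** All code ranges were expanded, reading S6691-6696 as S6691 to S6696.

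| List | Source | Distinct codes |
|---|---|---|
| Cancer-related surgery | SAP 8.3.2 table | 322 |
| Benign surgeries | SAP 8.4 table | 10 |
| Orthopedic surgeries | SAP 8.4 table | 31 |

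- Cancer and benign: one shared code, R3975.
- Cancer and orthopedic: none.
- Benign and orthopedic: none.

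The overlap is 1/10 = 10% of the benign codes and 1/322 = 0.3% of the cancer-surgery codes. These are shares of codes, not of procedures.

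**2. Is the condition stated anywhere for the Phase I event?** The 8.4 cancer-surgery row does not state it. The row for active cancer in the same table does write out the cancer codes together with the V codes. Protocol 9.3 names the operations but gives no codes for them as events. SAP section 10 adds no rule. The condition in criterion 7 is also tied to a window, "under cancer diagnosis with V code within the past 6 months from index date", whereas the Phase I event is dated from the treatment change. The sentence could therefore not be carried over whole without adaptation.

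**3. What each reading does to R3975.** Let n be the number of R3975 procedures in the 30-day windows, and k the number of these under a V-coded cancer diagnosis (0 ≤ k ≤ n).

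| Rule | Cancer row | Benign row | Sum |
|---|---|---|---|
| Literal pointer, no diagnosis needed | n | n | 2n |
| V-code condition read into the pointer | k | n | n + k |
| One sub-type by accompanying diagnosis | k | n − k | n |

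Compared with the last line:

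- The literal reading adds n − k procedures to the cancer row and k to the benign row, so all n are counted twice.
- The second reading leaves the cancer row at k but still adds k to the benign row, because the benign row has no exclusion.

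Reading the condition into the pointer therefore reduces the double count without removing it, unless k = 0. In the cohort without active cancer, R3975 without a V-coded cancer (n − k) is the part that the literal rule reports as cancer surgery.

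**4. Effect on the total.** Cancer and benign surgery are both sub-types of major surgery. A patient with an R3975 procedure has a major surgery under all three rules, so the overlap cannot change a patient-level count of any major surgery.

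**The case against.** The strongest reply is that the pointer names section 8.3.2, and that section uses the term together with the V-coded diagnosis. A careful programmer would meet the condition there. The presence of R3975 in both lists even fits that reading, since a non-specific code can sit in a cancer list if a diagnosis is also required. This stands to the extent that the literal reading is not the only one, and the SAP nowhere says that the condition is dropped. It does not settle the point, because R3975 under a V-coded cancer still matches both rows. The statement that a patient may contribute to several events does not help either: it allows several events per patient, but does not say which sub-type one procedure belongs to.

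A second reply is that the split may never be shown. Section 10 names only major surgery, and the SAP's list of 20 tables has no shell for events before treatment change. This also stands. The error appears only if sub-types are reported. But 8.4 defines the sub-types separately, and nothing later replaces that definition. New active cancer is a separate event with its V code written out, so a patient's cancer status does not depend on the surgery row alone.

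A reader might go further and infer three things that the documents do not support:

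- That benign operations are counted as cancer surgery throughout the list. The documents show benign use for R3975 only. They give no descriptions of the other 321 codes, so for those it remains a possibility opened by the missing condition.
- That the major-surgery total is wrong. This would need other listed codes to be used for benign operations outside the three named, which cannot be shown.
- That the list reaches beyond the 13 sites. The text names sites and the code row carries no site labels, so the two cannot be matched. This is an unreconciled definition, not a demonstrated excess.

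**Conclusion.** The point holds in a limited form. SAP 8.4 does not state whether cancer surgery requires a V-coded cancer diagnosis, and R3975 has no single sub-type under either reading of the pointer. If sub-types are reported, the cancer/benign split of surgery before treatment change is misstated, most clearly in the cohort without active cancer.

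The size is unknown. On the literal reading, the share of R3975 procedures wrongly placed in the cancer row is (n − k)/n. It can lie anywhere from 0 to 100%, and no figure in the documents narrows that range. Absence of a V code is also not proof of benign disease, because a cancer operation may be billed before the code is registered.

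The consequence is confined to the descriptive Phase I secondary objective. The Phase II bleeding comparison does not use this event definition and is not affected.

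**What to change.** In the SAP 8.4 code table:

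1. Define cancer surgery as a listed procedure performed under a V-coded cancer diagnosis, as in exclusion criterion 7. Tie the diagnosis to the operation rather than copying the six-month window before the index date.
2. State how brain tumors are handled. The text says tumors, not cancers, so a strict C-code plus V-code rule could drop operations that this wording may cover.
3. Reconcile the reused list with the sites named in the text, either by mapping codes to sites or by saying that the full list applies.
4. Assign R3975 by accompanying diagnosis to cancer surgery or to benign surgery, never to both.

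Items 1 and 4 are cheap: a few lines of text and a filter already specified for criterion 7. Items 2 and 3 need a decision and, if sites are enforced, a code-to-site mapping that the SAP does not yet contain.

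The downside is that a cancer operation billed before V-code registration would be missed or, for R3975, classed as benign.

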- Had a record of active cancer, defined as first diagnosis of cancer with V code (a special code applied to patients with confirmed diagnosis of cancer by Korean Ministry of Health and Welfare for reimbursement for 5 years or longer if recurrent/metastatic) within the past 6 months of period prior to index date; or receiving anti-cancer treatment (chemotherapy, radiation therapy, or cancer-related surgery) under cancer diagnosis with V code within the past 6 months period prior to index date

Follow-up

- **Phase I of the study:** Patients will be followed-up from the index date until the earliest of in-hospital death or end of the study period (31 Dec 2019).
- **Phase II of the study:** Patients will be followed-up from the index date until the earliest of outcome occurrence (bleeding event), treatment discontinuation, switch to another anticoagulant, in-hospital death, or end of the study period (31 Dec 2019), where patients will be considered to have discontinued treatment when new prescription is absent within the 30-day grace period after the end of the former prescription.

- **Variables**

Exposure(s)

- Anticoagulant therapy (PAC [LMWH, UFH, others], NOACs [apixaban, dabigatran, rivaroxaban, edoxaban], warfarin).

Outcome(s)

- **Phase I of the study:** sociodemographic and clinical characteristics of patients with VTE, utilization of index anticoagulant treatment, treatment patterns (including treatment interruption, switching, complete discontinuation), overall treatment duration, and clinical events preceding first treatment change
- **Phase II of the study:** Primary or secondary diagnosis with major bleeding (by site: intracranial, gastrointestinal [GI], and other sites) after the index date

Covariate(s)

- Sociodemographics (age, sex) will be assessed on the index date. Clinical characteristics including comorbidities, previous use of medications, and the number of outpatient visits will be assessed within the 6-month period prior to the index date

- **Data sources**

- South Korea's Health Insurance and Review Assessment Service (HIRA) database

- **Study size**

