- Overall anticoagulant treatment duration will be defined as the time period from the index date to the earliest of treatment interruption, switch, or discontinuation.
- If a patient has evidence of a repeat prescription within 30 days of the end of their prescription and does not experience any of the above events (treatment interruption, switch, or discontinuation), they will be assumed to be persistent on treatment.[21]
- Clinical event preceding first treatment change will be defined as occurrence of any event listed below within 30 days before treatment interruption, switch, or discontinuation. A new clinical event will be considered 'new' when it occurs for the first time within a 6-month period for acute conditions (arterial

thromboembolism, ischemic stroke, transient ischemic attack, myocardial infarction, angina pectoris, acute kidney injury, and abnormal liver function) and 5-years for chronic conditions (cancer, chronic kidney disease, and liver disease). A patient may contribute to multiple events.

- ① Major bleeding (as defined in Table 2)
- ② Complications of VTE: post-thrombotic syndrome and chronic thromboembolic pulmonary hypertension
- ③ Thromboembolism: PE diagnosis in patients with index event as DVT only, new diagnosis of arterial thromboembolism, ischemic stroke, transient ischemic attack, myocardial infarction, or angina pectoris
- ④ Major surgery: orthopedic surgeries (knee arthroplasty, hip arthroplasty, and hip fracture surgery), cancer surgeries (stomach, colorectal, hepatobiliary, pancreatic, breast, ovarian, cervical, renal, bladder, prostate, lung, and esophageal cancers, and brain tumors), and benign surgeries (myomectomy, oophorectomy, and transurethral resection of the prostate)
- ⑤ Cancer-related event (among non-active cancer patients only): new diagnosis of active cancer
- ⑥ Kidney function change: new diagnosis of chronic kidney disease or acute kidney injury
- ⑦ Liver function change: new diagnosis of liver disease or abnormal liver function

- **Phase II of the study**

- Major bleeding will be defined using primary or secondary diagnosis codes according to the ICD-10 diagnostic codes shown in Table 2 and classified by site (intracranial, gastrointestinal [GI], and other sites) [22].

Table 2. Definition of major bleeding by site

Major bleeding	ICD-10 diagnosis code	Diagnostic definition

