8.2. Study population

The study cohort will be defined as patients diagnosed with VTE between 1 Mar 2013 and 30 Jun 2019. The cohort entry will be defined as the date of incident VTE diagnosis. The index date will be defined as the date of first prescription for anticoagulants within 30 days after the index VTE event. The length of the exclusion assessment window will vary depending on the condition, from 12-months at minimum to anytime prior to index date. The following patients will be excluded: A record of VTE diagnosis within the 12-month period prior to the index VTE encounter, diagnosed with atrial fibrillation, atrial flutter, mechanical heart valve replacement or mitral stenosis anytime prior to index date, had a record of Inferior Vena Cava filter anytime prior to index date, received anticoagulatory therapy within the 12-month period prior to index VTE encounter to restrict to new users of anticoagulatory therapy, prescribed two different anticoagulants on the same index date to prevent exposure misclassification, had a record of pregnancy within the 9-month period prior to index date, and for the Phase II of the study only, had a record of active cancer within six months period prior to index date.

Baseline sociodemographic characteristics (e.g., age, sex) will be assessed on the index date, whereas clinical characteristics (comorbidities, previous use of medications, Charlson comorbidity index [CCI], HAS-BLED scores, initial presentation of VTE, number of outpatient visits) will be assessed in the 6-month period prior to the index date except when otherwise specified in section 8.4 *Variables* (Figure 2).

Within this study cohort, we will describe the treatment patterns of anticoagulants prescribed for VTE treatment throughout the period of follow-up, defined as the period from the index date to the end of the study period. Moreover, if feasible, we will also examine the risk of major bleeding overall and by site, associated with each NOAC use, as compared with warfarin.

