- In the NOAC-based group, all analyses will be repeated stratified by each individual NOAC class (e.g, apixaban, dabigatran, rivaroxaban, edoxaban) to

PFIZER CONFIDENTIAL

identify the difference in baseline characteristics and treatment patterns between each NOAC class.

- To identify potential reasons for treatment change, clinical events preceding the first treatment change (major bleeding, thromboembolism diagnosis, complications of VTE, major surgery, active cancer, a new diagnosis of CKD or AKI, a new diagnosis of liver disease or abnormal liver function) will be measured within 30 days prior to the first date of treatment change. Patients can contribute with multiple events.
- All analyses of treatment patterns will be presented stratified according to the index anticoagulant treatment, and not overall or per drug class.

Phase II of the study (comparative)

Propensity score analysis

- To balance and adjust for any potential differences in baseline sociodemographic and clinical characteristics between treatment groups, propensity score (PS) methods will be implemented.
 - A logistic regression model will be used to estimate the predicted probability (propensity) of initiating each NOAC compared with warfarin given baseline covariates mentioned above. By using the estimated PS, we will apply the PS based on the inverse probability of treatment weights (IPTW), where the treatment group of interest will be given a weight of 1/PS, and the comparator group will be given a weight of 1/(1-PS) [4, 5]. The most extreme 1% of PS values (IPTW with trimming) will be excluded to improve comparability between exposure groups.

Main Analysis

- Sociodemographic and clinical characteristics will be summarized with means (STD) or median (IQR) for continuous variables and with count (proportions) for categorical variables for the two treatment comparisons of: apixaban vs warfarin, rivaroxaban vs warfarin, edoxaban vs warfarin and dabigatran vs warfarin (and NOAC vs NOAC, if scientifically feasible).
 - Differences in baseline covariates between users of different OACs will be assessed using the SD where the absolute SD <0.1 will be considered as well balanced.
- The incidence rate of major bleeding overall and by site will be presented as the total number of events per 1,000 person-years, with its 95% CIs estimated using the Poisson distribution.

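### Seven codes in the 'Other bleeding' list name no site, so a GI or intracranial bleed can also be counted under 'All other sites' in Table 18

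*SAP*

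**What the plan says.** **Definition.** SAP 8.4 (Phase II outcome) states: "Major bleeding will be defined using primary or secondary diagnosis codes", with the codes "shown in below table and classified by site (intracranial, gastrointestinal [GI], all others". Protocol 9.3 gives the same lists in Table 2, describes the outcome as "classified by site (intracranial, gastrointestinal [GI], and other sites) [22", and so credits a published source. The protocol abstract words the outcome as "Primary or secondary diagnosis with major bleeding (by site: intracranial, gastrointestinal [GI], and other sites) after the index date".

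**Conditions for each row.** Each site has its own code list. Intracranial needs a code, an admission and a brain CT or MRI. GI and 'Other bleeding' need only a code and an admission. The 'Other bleeding' list opens with D62 and closes with "T792, T810, N950, R310, R311, R318, R58, T455, Y442, D683".

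**Event selection.** The one rule is on timing: "The earliest date of diagnosis of the major bleeding event after the index date will be defined as the outcome occurrence date". Follow-up ends at the first outcome.

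**Use of the sites.** SAP 8.2 says that, if feasible, "we will also examine the risk of major bleeding overall and by site, associated with each NOAC use, as compared with warfarin". SAP 10 says "The incidence rate of major bleeding overall and by site will be presented". The Table 18 shell has events, person-years, rates, and crude and weighted hazard ratios for intracranial, GI and all other sites.

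**The concern.** A reader will take the 'All other sites' block of Table 18 to describe bleeding outside the brain and the gut. Some codes that admit a patient to that block describe a consequence, a cause or a circumstance of bleeding, not a place. Such codes can sit as secondary diagnoses beside a bleed anywhere, and secondary diagnoses count.

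If one admission carries both a GI code and, say, D62, the written rule puts it in two rows. The GI count stays right, but the 'All other sites' count gains an event that belongs elsewhere. If NOAC effects relative to warfarin differ by site, the 'All other sites' hazard ratio is then pulled toward the GI or intracranial one.

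**Working it through.** The plan states no figure that depends on this point, so there is none to reproduce. The check has three parts.

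**1. Code counts** (SAP 8.4; identical in Protocol Table 2; N020-N029 taken as one entry)

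- Intracranial 10, GI 28, other 37. No code is shared between intracranial and other, or between GI and other.
- Entries in the 'other' list that name no anatomical site: D62 (acute posthaemorrhagic anaemia), R58 (haemorrhage not elsewhere classified), D683 (haemorrhagic disorder due to circulating anticoagulants), T455 (anticoagulant poisoning), Y442 (anticoagulant adverse effect), T792 (haemorrhage after trauma), T810 (haemorrhage complicating a procedure). That is 7/37 = 18.9%.
- The documents print codes without labels. The meanings are the ordinary ICD-10 ones and are an assumption here.

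Since the lists share no code, overlap arises only when one admission carries codes from two lists.

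**2. Rule applied to code patterns** (one admission, all codes on the same date)

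| Codes | Rows met as written | Rows met with the fix |
|---|---|---|
| K922 + D62 | GI and other | GI |
| K922 + T810 | GI and other | GI |
| I61 + R58, with CT/MRI | Intracranial and other | Intracranial |
| I61 + R58, no CT/MRI | Other | No site row |
| K922 + R310 | GI and other | GI and other (two named sites) |
| D62 alone | Other | Other |

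All six patterns are major bleeding overall under either rule, so Table 17 does not change.

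**3. What contamination could do: illustration on assumed inputs only**

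Assume 100 warfarin bleeds: 50 GI, 15 intracranial, 35 truly other. Let c be the share of GI and intracranial admissions that also carry a site-less code on the same date, equal in both arms. Treat the hazard ratio as the ratio of event counts at equal person-time.

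- 'Other' events on warfarin: 35 + 65c
- Share that are not other-site bleeds: 65c / (35 + 65c)
- Apparent 'other' HR: [35 × HR(other) + c × (50 × HR(GI) + 15 × HR(intracranial))] / (35 + 65c)

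| c | Share not other-site | Apparent HR if GI 0.5, intracranial 0.5, other 1.0 | Apparent HR if GI 1.0, intracranial 0.5, other 0.7 |
|---|---|---|---|
| 0 | 0 | 1.00 | 0.70 |
| 0.1 | 6.5/41.5 = 16% | 38.25/41.5 = 0.92 | 30.25/41.5 = 0.73 |
| 0.3 | 19.5/54.5 = 36% | 44.75/54.5 = 0.82 | 41.75/54.5 = 0.77 |
| 0.5 | 32.5/67.5 = 48% | 51.25/67.5 = 0.76 | 53.25/67.5 = 0.79 |

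The first set of hazard ratios moves the 'other' result down and the second moves it up. The three site counts would sum to 1.06, 1.20 and 1.32 times the overall count at c = 0.1, 0.3 and 0.5 (1 + 0.65c, rounded down from 1.065, 1.195 and 1.325 to within 0.01). None of these inputs is in the documents.

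**The case against.** **The third class may be a residual.** Sorting bleeds into intracranial, GI and all others ordinarily means a partition, and the source cited in Protocol 9.3 may contain an allocation rule. That is a fair reading of intent. But neither document writes the rule down, and the row has its own code list and its own admission criterion. The HAS-BLED table in SAP 8.4 uses the same codes for bleeding history and labels them as other sites. A programmer who follows the text would build a list, not a residual.

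**The earliest-date rule may settle many cases.** A reader might infer that every GI or intracranial admission with one of the seven codes adds an event to 'All other sites'. The documents do not support that. If Table 18 splits the first bleed by site, codes with different dates resolve to the earliest one, and only same-date codes stay in two rows. The plan does not say whether Table 18 splits the first bleed or runs a separate first-event analysis for each site. So the point is stated for same-date codes.

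**The by-site results are secondary and conditional.** Phase II depends on power, and SAP 8.2 makes the bleeding comparison subject to feasibility. This stands and limits the weight of the point. It does not remove the fault if Table 18 is produced.

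**The fix leaves a gap.** An intracranial code without imaging plus one of the seven codes loses its site row. That is true, and the footnote should say so. The present rule gives such an event a row, but one labelled as bleeding elsewhere.

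**Conclusion.** The point holds for the by-site results only. As written, a GI or intracranial bleeding admission with a same-date code from the seven counts in its own row and also in 'All other sites'. That row's rate and hazard ratio can therefore include bleeds at the two named sites.

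Size and direction are unknown: the documents give no co-coding frequency, no site split and no site-specific hazard ratio. Two further inferences should be resisted. First, 7 of 37 is a share of list entries, not of events, so it does not mean that 19% of 'other' bleeds are misplaced. Second, the overall result is not biased by this overlap: the admission is already a major bleed, so Table 17, the overall hazard ratio and the sample sizes stand. With same-date codes the GI or intracranial event is double-counted, not lost from its own row.

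The conclusion rests on the ordinary ICD-10 meanings of the seven codes and on the absence of any site-allocation rule in either document.

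**What to change.** Add to SAP 8.4 and Protocol 9.3, Table 2: 'For the by-site analysis, D62, R58, D683, T455, Y442, T792 and T810 count as other sites only when the same admission carries no intracranial or GI bleeding code.' Leave the overall major bleeding definition unchanged.

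Add a Table 18 footnote with two statements:

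- An admission with codes naming two different sites counts in both rows, so the rows need not sum to Table 17.
- An intracranial code without CT/MRI plus one of the seven codes appears in Table 17 but in no site row.

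The cost is one sentence in each document, one footnote and a few lines of code on data already extracted. The downside is a slightly smaller 'other sites' count and a few events with no site row.
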